#### **5.4.1.3 Supplementary analysis under estimand 2**

The same imputation model as specified in [Appendix 5.4.1.1](#) will be used in supplementary analysis 1. Again, multiple imputation will be used to account for uncertainty in the imputation process and there will be 100 multiply imputed datasets. The results from these 100 imputed datasets will be combined using Rubin's method. Further details are provided below.

1. In this step, the control-based PMM will be used. With this imputation model, the missing value in the inclisiran group will not be constructed from the observed data in the inclisiran group but rather from the observed and imputed data in the control group. SAS PROC MI will be utilized using the FCS REG statement, where only previous measurements will be included for each imputed variable. The MNAR statement in SAS PROC MI will also be used under MNAR assumption for inclisiran group. After this step, the 100 datasets (out\_step1) will be fully imputed.
2. Datasets (out\_step1) will be used in this step. If there are enough RDO data, the RDO based imputation model will be utilized in this step. Thus, for participants handled by intercurrent events of treatment discontinuation, if the LDL-C value is missing before step 1 and after treatment discontinuation, set this value back to missing. Then, SAS PROC MI will be utilized using the FCS REG statement, where previous measurements and an indicator of on- or off-treatment status at the same visit with the response will be included for each imputed variable. This imputation will be implemented based on data within each group. After this step, the 100 datasets (out\_step2) will be fully imputed.
3. If step 2 is conducted, then datasets (out\_step2) will be used in this step. Otherwise, datasets (out\_step1) will be used. For participants who died, set the values after death using his/hers baseline value. (out\_step3)
4. Datasets (out\_step3) will be used in this step. The absolute change and the percentage change values will be calculated in each of the imputed datasets.
5. These 100 datasets will be analyzed using the ANCOVA model for the LDL-C endpoints.
6. The results from the 100 datasets will be combined using Rubin's method via SAS PROC MIANALYZE procedure.

## 5.4.2 Analysis supporting secondary objective(s)

### Objectives for core part

The same imputation models and procedure as specified in [Appendix 5.4.1.1](#) will be applied to all secondary efficacy endpoints for core part. For Lp(a), log-transformation will be taken before the imputation and the imputation model will exclude variables at Day 30 and Day 90 visits.

### Objectives for extension part

The RDO based imputation model is the same as specified in [Appendix 5.4.1.1](#) except that the model here is extended to include more measurements at Day 210, Day 270, Day 330 and Day 360.

For the control-based PMM, the same model as specified in [Appendix 5.4.1.1](#) will be used for fitting the imputation model based on data from control group (i.e., the measurements at baseline, Day 30, 90, 150 and 180 from control group will be used to fit the imputation model). Based on the fitted regression model, the imputation model for missing measurements at Day 330 after specific intercurrent events in inclisiran group will only include following as covariates:

- Baseline value of efficacy measurement (continuous)
- Observed/imputed value of efficacy measurement at Day 30 (continuous)
- Observed/imputed value of efficacy measurement at Day 90 (continuous)
- Observed/imputed value of efficacy measurement at Day 150 (continuous)

In other words, the imputed Day 180 values in inclisiran group under the control-based PMM will be carried forward as imputations for missing measurements at Day 330 in inclisiran group.

1. Only inclisiran group data will be included. For those participants who experienced the intercurrent event of using prohibited LLT, set the LDL-C values on or after the usage of LLT missing (out\_step1).
2. Missing data will be imputed under MAR assumption in this step. The same imputation model as specified for fitting purpose in the control-based PMM will be used. SAS PROC MI will be utilized using the FCS REG statement, where only previous measurements will be included for each imputed variable. A total of 100 datasets (out\_step2) will be created. These fully imputed datasets will be utilized in step 3.
3. For participants handled by intercurrent events of treatment discontinuation, if the measurement is missing in (out\_step1) and after treatment discontinuation, set this value back to missing (out\_step3). These datasets (out\_step3) will be utilized in step 4.
4. If there are enough RDO data, the RDO based imputation model as specified will be used in this step. SAS PROC MI will be utilized using the FCS REG statement, where previous measurements and an indicator of on- or off-treatment status at the same visit with the response will be included for each imputed variable. This imputation will be implemented based on data in inclisiran group. If there are not enough RDO data, the control-based

PMM will be used in this step. With this imputation model, the missing value in the inclisiran group will not be constructed from the observed data in the inclisiran group but rather from the observed (excluding data after usage of LLT) and imputed data in the control group. SAS PROC MI will be utilized using the FCS REG statement. The MNAR statement in SAS PROC MI will also be used under MNAR assumption for inclisiran group. These datasets(out\_step4) will be utilized in step 5.

5. For participants who died, set the values after death using his/hers baseline value. (out\_step5)
6. Datasets (out\_step5) will be used in this step. The absolute change and the percentage change values will be calculated in each of the imputed datasets.
7. These 100 datasets will be analyzed descriptively for the LDL-C endpoints.
8. The results from the 100 datasets will be combined using Rubin's method via SAS PROC MIANALYZE procedure.

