4.3.1 Rationale for study duration

The study primary endpoint will be assessed at Day 150, after 2 injections of inclisiran/placebo on Day 1 and Day 90. It is supported with:

- ORION-1 demonstrated that 2 injections on Day 1 and on Day 90 produced a significant percentage LDL-C reduction of 52.6% at Day 180
- In ORION-9, -10 and -11, 2 initial injections (Day 1 and Day 90) led to a similar percentage reduction in LDL-C at Day 150. The magnitude of this reduction was then maintained with subsequent injections every 6 months
- No difference was observed in PK/PD between Chinese and non-Chinese population in ORION-14
- ORION-18 showed the consistency of efficacy with ORION-9, -10 and -11 in Chinese population with a significant percentage LDL-C reduction at Day 150. The magnitude of this reduction was also maintained in the following visit after the third injection at Day 330.

Based on the above data, a 180-day duration of the core part with 2 injections is deemed as sufficient for evaluating the effect of inclisiran as monotherapy, compared with placebo. The primary endpoint will be assessed on Day 150, which is expected to be the nadir of LDL-C lowering effect. In addition, this duration will leave placebo-treated participants with the shortest unprotected period of no LLT covered.

The duration with both core part and extension part is also suitable to assess the longer-term efficacy as well as safety and tolerability. The additional treatment administered in an extension part of the study is suitable to collect meaningful additional long-term data on inclisiran, which will be assessed as secondary [REDACTED].

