### 2.6.3.2 Estimands for extension part

The secondary efficacy analysis for extension part will account for different intercurrent events as explained in the following:

- **Discontinuation of study treatment:** Retrieved drop out (RDO) data collected after discontinuation from study treatment will be used for the analysis (treatment policy). Missing data after discontinuation from study treatment will be multiply imputed based on RDO data, and when there are no sufficient RDO data, a control-based PMM (using the Core Part data) will be used for multiple imputation. The detailed information is specified in [Appendix 5.4.2](#).
- **Use of prohibited LLT:** Use of prohibited LLT (PCSK9 monoclonal antibodies taken before Day 330 visit assessment or other LLT taken within 30 days before Day 330 visit assessment) will be treated in a hypothetical scenario of what would happen had those LLT not been taken, and those participants behaved like other participants in the same treatment group (hypothetical strategy). Data after those intercurrent events will be excluded for the analysis and will be multiply imputed under MAR assumption.
- **Death:** Death due to CV or non-CV causes is considered as an unfavorable outcome (composite strategy). The LDL-C values at Day 330 after death will be set using the participant's baseline values.

In the case of multiple intercurrent events, death will be the dominant one in the analysis (if present). If a participant experiences only two other intercurrent events and usage of prohibited LLT occurs first, s/he will be handled by the event of usage of LLT (hypothetical strategy). If treatment discontinuation occurs prior to usage of prohibited LLT, then data after usage of LLT will be set missing and s/he will be handled by the event of treatment discontinuation (treatment policy). The detailed imputation model and algorithm are specified in [Appendix 5.4.2](#). Number and percentage of participants by each intercurrent event will be summarized by treatment group in final analyses. Listing will also be provided.

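### The control-based fallback for Day 330 LDL-C ignores a discontinued participant's own observed Day 180, 210 and 270 values

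*SAP*

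**What the plan says.** The Day 330 endpoints (percentage and absolute change in LDL-C, Inclisiran Group only) are descriptive: a mean with a 95% confidence interval (SAP 2.6.1.2). Treatment discontinuation is handled by treatment policy (SAP 1.2.2.2).

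Observed values after discontinuation are used as they stand. Missing ones are imputed from RDO data. If those are insufficient, "a control-based PMM (using the Core Part data) will be used for multiple imputation" (SAP 2.6.3.2).

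SAP 5.4.2, extension part, defines the two imputation models:

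- **RDO model:** "the model here is extended to include more measurements at Day 210, Day 270, Day 330 and Day 360".
- **Control-based model, fitting:** "the measurements at baseline, Day 30, 90, 150 and 180 from control group will be used to fit the imputation model".
- **Control-based model, applying:** "the imputation model for missing measurements at Day 330 after specific intercurrent events in inclisiran group will only include following as covariates". The list that follows is baseline, Day 30, Day 90 and Day 150, each post-baseline value observed or imputed.
- **Carry-forward:** "the imputed Day 180 values in inclisiran group under the control-based PMM will be carried forward as imputations for missing measurements at Day 330".

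Step 1 of the algorithm states "Only inclisiran group data will be included", while step 4 builds the control-based imputations from control-group data. Protocol 4.3.1 describes Day 150 as the time point "which is expected to be the nadir of LDL-C lowering effect".

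**The concern.** Under treatment policy, a participant who stops should contribute their actual course after stopping. LDL-C measured after the last active dose is the best evidence of that course. For someone who discontinues before the Day 270 dose, the last active dose was on Day 90 at the latest, 240 days before Day 330.

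The fallback's last predictor is Day 150, the expected low point. Its Day 180 prediction is then used 150 days later. Visits on Days 180, 210 and 270 may lie in between, but their results do not enter. LDL-C at Day 270 could still be halved or be back at baseline, and the Day 330 prediction would not change.

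The same happens to a final Early Exit sample. SAP Table 2-1 maps an Early Exit after Day 150, 180 or 210 to Day 180, 210 or 270, and this rule uses none of those visits.

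Day 330 is the only extension-part efficacy time point among the secondary endpoints, and it has no concurrent untreated arm. The tipping-point analysis in SAP 2.6.5 covers Day 150 LDL-C only, so no planned sensitivity analysis would show the effect of this rule.

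**Working it through.** The plan gives no figure for this imputation, so there is none to reproduce. The check compares the planned rule with a control regression that has the same time gap and uses the participant's observed Day 270 value.

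**Inputs**
- Predictor list and carry-forward: SAP 5.4.2.
- Assumed own values: -42%, -45% and -50% at Days 30, 90 and 150. The documents report reductions of about 48% to 57% in earlier phase 3 trials (Protocol 2.2).
- Assumed control group: flat mean, equal variances, and correlation ρ either exchangeable (0.4 to 0.85) or autoregressive (0.85 to 0.95 per month). The documents give no correlations.
- Assumed Day 270 values: -10%, -30%, -40% and -45%.

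All figures are mean predictions, before the random draw of multiple imputation.

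**Planned rule** (Day 180 on baseline and Days 30, 90, 150)
- Exchangeable: each of four predictors has weight ρ/(1+3ρ). The deviations sum to 0-42-45-50 = -137. At ρ = 0.4: -137 × 0.4/2.2 = -24.9%. At ρ = 0.85: -137 × 0.85/3.55 = -32.8%.
- Autoregressive: only Day 150 counts, one month back, so the prediction is ρ × (-50): -42.5% at 0.85 and -47.5% at 0.95.

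**Gap-matched rule** (Day 150 on baseline and Day 90, a 60-day gap like Day 270 to Day 330, with observed Day 270 in the Day 90 slot)
- Exchangeable: weight ρ/(1+ρ), 0.286 at 0.4 and 0.459 at 0.85.
- Autoregressive over two months: weight ρ², 0.7225 at 0.85 and 0.9025 at 0.95.

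| Correlation | Planned | Matched, Day 270 = -10% | -30% | -40% | -45% |
|---|---|---|---|---|---|
| Exch. 0.40 | -24.9 | -2.9 | -8.6 | -11.4 | -12.9 |
| Exch. 0.55 | -28.4 | -3.5 | -10.6 | -14.2 | -16.0 |
| Exch. 0.70 | -30.9 | -4.1 | -12.4 | -16.5 | -18.5 |
| Exch. 0.85 | -32.8 | -4.6 | -13.8 | -18.4 | -20.7 |
| AR 0.85 | -42.5 | -7.2 | -21.7 | -28.9 | -32.5 |
| AR 0.90 | -45.0 | -8.1 | -24.3 | -32.4 | -36.5 |
| AR 0.95 | -47.5 | -9.0 | -27.1 | -36.1 | -40.6 |

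**Gap between the rules**
- Day 270 at -30% to -10%: from 24.9-8.6 = 16.3 to 47.5-9.0 = 38.5 points.
- Day 270 at -45% to -40%: from 47.5-40.6 = 6.9 to 30.9-16.5, about 14 points.

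**Check under other assumptions.** Take -50% at Days 30, 90 and 150, correlation 0.5 to 0.9 (exchangeable, or autoregressive by visit), and own Day 180, 210 and 270 values in the last three predictor slots, starting from -45% at Day 180. The planned rule gives -25% to -45%. The gap is about 9 to 36 points if own values reach -25% or -10% by Day 270, and about 5 to 9 points if Day 270 is -40%.

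**Earlier leavers**, same assumptions. Missing Day 90 and 150 values are themselves predicted from the control regression, so carry-over shrinks:
- Days 30 and 90 observed: -12.5% to -40.5%.
- Day 30 only: about -6% to -36.5%.
- No post-baseline value: 0%.

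**Arm mean.** With about 100 participants in the group, one affected participant moves the Day 330 mean by 0.16 to 0.39 points if effect has been lost (16 to 39 divided by 100), and by about 0.07 to 0.14 points if it is largely kept.

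**The case against.** **It is a fallback, and few may reach it.** This stands. The rule needs insufficient RDO data. Participants who discontinue treatment are asked to keep attending, and an observed Day 330 value is used directly. An Early Exit after Day 270 is mapped to Day 330 and counts as observed. A participant who has had the Day 270 dose has completed planned treatment, so a missing Day 330 value falls under missing at random. However, the SAP sets no threshold for enough RDO data, and in a group of about 100 there may be few retrieved drop-outs.

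**Untreated control data end at Day 180.** True, because the Control Group then receives inclisiran. That justifies fitting on core-part data. It does not justify leaving out the participant's own later values, which can be applied to a control regression of equal gap.

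**The effect may last.** Protocol 4.3 reports, from an earlier phase 2 trial, a similar reduction at Day 270 and Day 90. If so, the two rules differ less, and the gap is not an error against the truth: for someone still at -40%, an imputed -25% to -33% is not flattering. The favourable direction is established only where LDL-C has risen.

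**Stronger readings.** A reader might infer that early stoppers in general are imputed as still strongly treated. The documents do not support this, because carry-over falls to zero for someone with no post-baseline value. A reader might also infer from step 1 that the control records are lost and the model cannot be fitted. The fitting sentence and step 4 both say that control data are used, so this is a drafting point.

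**Conclusion.** The point holds within limits. It concerns Inclisiran Group participants with on-treatment values through Day 150 who then discontinue before the Day 270 dose, have at least one LDL-C value after Day 150 and lack Day 330, and it arises only if the fallback is triggered. For them the rule disregards observed post-discontinuation data, which does not fit a treatment-policy estimand, and it overstates durability if LDL-C has risen since Day 150.

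The gap from a gap-matched control regression is about 16 to 39 points per such participant if Day 270 is -30% to -10%, and about 7 to 14 points if it is -45% to -40%. These sizes rest on an assumed trajectory, a flat control mean and assumed correlations. They measure the difference between two rules. Day 330 is descriptive, and the primary Day 150 analysis does not depend on it.

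**What to change.** Revise the extension-part text of SAP 5.4.2:

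1. If a value after Day 150 was observed, impute Day 330 from baseline and the latest own value, using the control-group core-part regression with the matching gap:
   - latest Day 270: Day 150 on baseline and Day 90 (60 days);
   - latest Day 210: Day 150 on baseline and Day 30 (120 days);
   - latest Day 180: Day 180 on baseline and Day 30 (150 days).
2. Count an Early Exit sample mapped to one of these visits as observed.
3. Keep the present rule where nothing after Day 150 was observed. Those longer gaps have no matching control regression from an observed post-baseline value.
4. Add a return-to-baseline sensitivity analysis for Day 330.
5. State in step 1 that control-group core-part records are kept for fitting in step 4.

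The cost is SAP wording and a little more programming, since all values are already collected. The Day 330 mean may come out slightly less favourable.

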## 5.4 Statistical models

### 5.4.1 Analysis supporting primary objective(s)

#### 5.4.1.1 Primary efficacy analysis

In handling of intercurrent events and missing data not related to intercurrent events, multiple imputation will be used to account for uncertainty in the imputation process and there will be 100 multiply imputed datasets. The results from these 100 imputed datasets will be combined using Rubin's method. Further details are provided below.

For control-based PMM, the missing data after specific intercurrent events in inclisiran group will be imputed using data from control group. The covariates and baseline characteristics which can be predictive of the response will be included in a multiple imputation procedure (SAS PROC MI) and will include the following:

- Baseline value of efficacy measurement (continuous)
- Observed/imputed value of efficacy measurement at Day 30 (continuous)
- Observed/imputed value of efficacy measurement at Day 90 (continuous)
- Observed/imputed value of efficacy measurement at Day 150 (continuous)
- Observed/imputed value of efficacy measurement at Day 180 (continuous)

[figure not shown]
For RDO based imputation model, the missing data after treatment discontinuation will be imputed based on RDO data within each group. The covariates, baseline characteristics and on- or off- treatment status at the same visit with the response which can be predictive of the response will be included in a multiple imputation procedure (SAS PROC MI) and will include the following:

- Baseline value of efficacy measurement (continuous)
- Observed/imputed value of efficacy measurement at Day 30 (continuous)
- Observed/imputed value of efficacy measurement at Day 90 (continuous)
- Observed/imputed value of efficacy measurement at Day 150 (continuous)
- Indicator of on- or off- treatment status at Day 180 (binary)
- Observed/imputed value of efficacy measurement at Day 180 (continuous)

The indicator variable will vary with the imputed response from visit to visit.

1. For those participants who experienced the intercurrent event of using prohibited LLT, set the LDL-C values on or after the usage of LLT missing (out\_step1).

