2. Missing data will be imputed under MAR assumption in this step. The same imputation model as specified for control-based PMM will be used except that the missing data will be multiply imputed using data within each treatment group. SAS PROC MI will be utilized using the FCS REG statement, where only previous measurements will be included for each imputed variable. A total of 100 datasets (out\_step2) will be created. These fully imputed datasets will be utilized in step 3.

3. For participants handled by intercurrent events of treatment discontinuation, if the measurement is missing in (out\_step1) and after treatment discontinuation, set this value back to missing (out\_step3). These datasets (out\_step3) will be utilized in step 4.
4. If there are enough RDO data, the RDO based imputation model will be used in this step. SAS PROC MI will be utilized using the FCS REG statement, where previous measurements and an indicator of on- or off-treatment status at the same visit with the response will be included for each imputed variable. This imputation will be implemented based on data within each group. If there are not enough RDO data, the control-based PMM will be used in this step. With this imputation model, the missing value in the inclisiran group will not be constructed from the observed data in the inclisiran group but rather from the observed and imputed data in the control group. SAS PROC MI will be utilized using the FCS REG statement, where only previous measurements will be included for each imputed variable. The MNAR statement in SAS PROC MI will also be used under MNAR assumption for inclisiran group. After this step, the 100 datasets(out\_step4) will be fully imputed. These datasets will be utilized in step 5. (Which model will be used in this step will be determined before Core Part database lock)
5. For participants who died, set the values after death using his/hers baseline value. (out\_step5)
6. Datasets (out\_step5) will be used in this step. The absolute change and the percentage change values will be calculated in each of the imputed datasets.
7. These 100 datasets will be analyzed using the ANCOVA model for the LDL-C endpoints.
8. The results from the 100 datasets will be combined using Rubin's method via SAS PROC MIANALYZE procedure.

#### 5.4.1.2 Supplementary analysis under estimand 1

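### The only MAR step for Day 330 LDL-C (SAP 5.4.2, extension part, step 2) names an imputation model that stops at Day 180

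*SAP*

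**What the plan says.** The extension-part efficacy endpoints are percentage and absolute change in LDL-C at Day 330 in the inclisiran group, analysed descriptively with 95% confidence intervals (SAP 2.6.1.2).

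Two classes of Day 330 value are to be imputed under MAR:

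- After prohibited LLT, SAP 2.6.3.2 states: "Data after those intercurrent events will be excluded for the analysis and will be multiply imputed under MAR assumption". The strategy is hypothetical: these participants are taken to behave like others in their own treatment group.
- SAP 2.6.4.2 sets the same assumption for missing values not related to an intercurrent event.

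Both sections refer to Appendix 5.4.2 for the model and algorithm. In its extension part, step 2 is the only step that imputes under MAR: "The same imputation model as specified for fitting purpose in the control-based PMM will be used". The text above the steps defines that fitting model: "the measurements at baseline, Day 30, 90, 150 and 180 from control group will be used to fit the imputation model". Of the step 2 output the SAP says: "These fully imputed datasets will be utilized in step 3". Step 3 then begins: "For participants handled by intercurrent events of treatment discontinuation, if the measurement is missing in", and sets only such post-discontinuation values back to missing. Step 4 imputes either with the retrieved drop-out (RDO) model or, if RDO data are too few, with the control-based pattern-mixture model (PMM).

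**The concern.** A regression sequence can impute only the variables it contains. If the MAR model ends at Day 180, no Day 330 value is imputed in step 2, and its output is not fully imputed for the one visit that defines the endpoints. The MAR-handled values then arrive at step 4 still missing, where nothing was written for them.

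At stake is whether the estimate follows its own estimand. A participant who took a prohibited LLT, or who simply missed the Day 330 sample, should receive a value like those of other inclisiran participants. A control-based draw instead gives a value closer to placebo, and so understates the reduction. Leaving the value missing means the imputation of the endpoint is incomplete. Two programmers could follow the text and obtain different results.

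**Working it through.** **1. Which visits each model holds**

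| Model | Where used | Time points | Day 330 included? |
|---|---|---|---|
| Core-part MAR model (5.4.1.1) | Core step 2 | Baseline, 30, 90, 150, 180 (5) | Not needed; endpoint is Day 150, which is included |
| Fitting model of the control-based PMM (5.4.2) | Extension step 2 | Baseline, 30, 90, 150, 180 (5) | No |
| Extended RDO model (5.4.2) | Extension step 4 | The same 5 plus 210, 270, 330, 360 (9) | Yes |

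The step 2 model has 5 of the 9 time points and none of the 4 after Day 180. The SAP extends only the RDO model.

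**2. Comparison with the core part.** Core step 2 is worded in parallel: "The same imputation model as specified for control-based PMM will be used except that the missing data will be multiply imputed" within each treatment group. It works there because the list contains the Day 150 endpoint. In the extension part the endpoint moved to Day 330 and the list did not.

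**3. What reaches step 4.** Step 3 resets only values missing after treatment discontinuation. MAR-handled Day 330 values are untouched by step 3 and were not filled in step 2, so they enter step 4 missing.

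- *RDO branch.* The model contains Day 330 and would fill them, though it is the discontinuation model. It is fitted in the inclisiran group with an on/off-treatment indicator, so the practical difference from MAR may be small.
- *Control-based branch.* One sentence limits the Day 330 draws to missing values after specific intercurrent events; on that reading the values stay missing. The carry-forward sentence that follows and the wording of step 4 refer to missing inclisiran values without the limit; on that reading they receive control-based draws.

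Borrowing the Day 180 carry-forward for the MAR values would not solve this. It is stated only for the control-based PMM. Day 180 is also 90 days after the Day 90 dose, whereas Day 330 is 60 days after the Day 270 dose.

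**4. Illustrative size, control-based reading only.** The documents give no figure to reproduce and no missing-data rate. Inputs:

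- −57.2% at Day 330, from the Phase 3 study in Asian patients (Protocol 2.2). It is placebo-adjusted and from a higher-risk population; using it as the within-group change here is an assumption.
- 100 inclisiran participants (Protocol 6.1.2).
- Assumed: mean control change of zero, equal SDs, one common correlation ρ between all core time points, and a participant with average baseline who is at −57.2% on Days 30, 90 and 150.

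With four equally correlated predictors (baseline and three visits), each regression coefficient is ρ/(1 + 3ρ). The predicted control-based change is 3 × ρ/(1 + 3ρ) × (−57.2%).

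| ρ | Coefficient | Control-based change | Gap from −57.2% | Shift in mean per value (gap/100) |
|---|---|---|---|---|
| 0.3 | 0.158 | −27.1% | 30.1 | 0.301 |
| 0.5 | 0.200 | −34.3% | 22.9 | 0.229 |
| 0.7 | 0.226 | −38.7% | 18.5 | 0.185 |
| 0.9 | 0.243 | −41.7% | 15.5 | 0.155 |

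The outer limit, a fully placebo-like draw, is 57.2/100 = 0.57 points per value. For an assumed 5 affected participants the shift is 5 × 0.155 to 5 × 0.301, or about 0.8 to 1.5 points, with an outer limit of 5 × 0.572 = 2.9. All shifts are toward a smaller reduction.

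**The case against.** The intent can be inferred. Step 1 restricts the data to the inclisiran group, step 2 uses only previous measurements and calls its output fully imputed, and step 3 sets values back to missing, which presupposes that step 2 had filled them. The consistent reading is a sequential within-group regression through Day 330. On that view this is an incomplete cross-reference. The control-based reading can also be called strained: SAP 2.6.3.2 confines the PMM to data missing after treatment discontinuation, and the carry-forward sentence is introduced as a restatement of a sentence that carries the limit. Core step 4 has similarly unrestricted wording and causes no trouble there. The numerical range rests on assumptions throughout.

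Much of this is fair. A regression through Day 330 is probably what was meant, the RDO branch is likely to do little harm, and material bias needs literal use of step 2, too few RDO data and the broad PMM reading all at once. But no sentence states the presumed intent, and step 2 expressly selects the model that ends at Day 180. The comparison with core step 4 does not help: core step 2 has already filled every value that step 3 does not reset, so unrestricted wording there has nothing else to act on. In the extension part it does.

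**Conclusion.** The concern holds. As written, step 2 cannot deliver the MAR imputation of Day 330 LDL-C that SAP 2.6.3.2 and 2.6.4.2 require, and its output is wrongly described as fully imputed. This rests on the text alone and is certain. What would happen next is less certain, because it depends on which step 4 branch is chosen and how it is read.

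The size of the effect cannot be established from the documents. The 0.15 to 0.30 points per affected value applies only to the control-based reading and depends on every assumption listed in the check. The scope is limited to two single-group, descriptive secondary endpoints; the Day 150 primary analysis and its test are unaffected. They are, however, the only secondary efficacy endpoints of the extension part, so the algorithm should be corrected.

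**What to change.** In step 2 of SAP 5.4.2 (extension part), replace the reference to the PMM fitting model with an explicit statement along these lines: missing data are imputed under MAR within the inclisiran group using FCS REG, with previous measurements entered sequentially over baseline and Days 30, 90, 150, 180, 210, 270 and 330 (8 time points), without the on/off-treatment indicator. Day 360 may be listed as well; because only earlier measurements are predictors, it does not affect Day 330.

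Keep the model ending at Day 180 solely for the control-based PMM in step 4, and state that step 4, in either branch, applies only to values set back to missing in step 3.

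The cost is one or two sentences in the SAP and the matching programming before final database lock. No new data are needed.
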